11.4. Protocol Deviations

Unless there is a safety concern, there should be no deviations or violations of the study protocol. In the event of a safety concern, the Investigator or designee must document and explain the reason for any deviation from the approved protocol. The Investigator may implement a deviation from, or a change to, the protocol to eliminate an immediate hazard to study participants without prior IRB/IEC approval. Immediately after the implemented deviation or change, the Investigator must submit a report explaining the reasons for the protocol violation or deviation to the IRB/IEC, FibroGen, and to the regulatory authorities, if required.

11.5. Retention of Data

A FibroGen representative will inform the Investigator in writing when it is acceptable to dispose of any study records. To enable evaluation and/or audits from regulatory authorities or FibroGen or designee, the Investigator agrees to keep records, including the identity of all participating subjects (eg, subject identification code list and all source documents), all original signed ICFs, copies of all CRFs, original laboratory reports, detailed records of drug disposition and all essential documents for the conduct of a clinical study. To comply with international regulations, the records should be retained by the Investigator for at least 2 years after the last approval of a marketing application in an ICH region and until there are no pending or contemplated marketing applications in an ICH region, or until at least 2 years have elapsed since the formal discontinuation of clinical development of the investigational product. However, the Investigator may need to retain these documents for a longer period if required by applicable law, regulatory requirements or by an agreement with FibroGen whichever is longer.

11.6. Financial Disclosure

The Investigator's disclosable financial interests must be obtained prior to initiation of the study site, at completion of the study at the investigational site, and 1 year following study completion.

The Investigator should promptly update this information if any relevant changes occur during the above described period.

Disclosable financial interests will be recorded on the Investigator Financial Disclosure Form.

Any Investigator(s) added as investigational staff to the form FDA 1572 or other qualified investigator statement must complete the Investigator Financial Disclosure Form at the beginning of his/her participation in the study. The Investigator Financial Disclosure Form for any Investigator(s) leaving the clinical site prior to study completion will be obtained prior to study completion.

12. PUBLICATION POLICY

The data and results of the study will be owned solely by FibroGen and shall be confidential information of FibroGen, subject to the Investigator's publication rights, described below and if any outlined in the Clinical Trial Agreement. It is understood by the Investigator that FibroGen may use the information developed in this clinical study in connection with the development of its compounds and therefore, may disclose it as required to other clinical investigators, the Licensing Authority or to regulatory agencies of other governments. To allow for the use of the information derived from this clinical study, the Investigator understands that he/she has an obligation to provide and disclose test results and all data developed during this study to FibroGen.

Any publication or presentation of the results of this clinical study by the Investigator may only be made in strict compliance with the provisions of the Clinical Trial Agreement. Any publication relating to the study shall be made in collaboration with FibroGen. The Investigator should understand that it is not FibroGen's intention to prevent publication of the data generated in the clinical study. However, FibroGen reserves the right to control the form and timing of such publication for commercial reasons. The Study Center and Investigator shall adhere to the publication language as outlined in both Clinical Trial Agreement and the protocol to the extent that if there is any conflict or ambiguity between Clinical Trial Agreement and the protocol, the publication terms in the Clinical Trial Agreement shall prevail.

14. APPENDICES

APPENDIX 1. SCHEDULE OF ASSESSMENTS

Study Week	Screening Period (Up to 6 Weeks) ^a	Dosing Period ^{a, b, c} (48 Weeks)																	Safety Follow-Up Period			
		Day 1 (First dose)	3	6	9	12	15	18	21	24	27	30	33	36	39	42	45	48/ Last dose/ET ^t	28 days after last dose ^r	60 days after last dose phone call ^r		
Assessment		Pre-dose	Post-dose																			
Sign and date ICF	X																		X ^s			
Eligibility Assessment (Inclusion/Exclusion)	X	X																				
Demographics	X																					
Medical History	X																					
Labs	X	X				X				X				X					X	X		
TB test ^u (For Czech Republic Only)	X																					
Vital Signs ^v	X	X	X	X	X	X	X	X	X	X	X	X	X	X	X	X	X	X	X	X	X	
Physical Exam ^{d, e}	X ^d	X ^d				X ^d				X ^d				X ^d					X ^d			
ECG ^f	X																		X			
Randomization		X																				
Infusions ^{g, h, v}			X	X	X	X	X	X	X	X	X	X	X	X	X	X	X	X	X	X ^t		
Adverse Events ⁱ	X	X	X	X	X	X	X	X	X	X	X	X	X	X	X	X	X	X	X	X	X	X
Concomitant Medications ^j	X	X	X	X	X	X	X	X	X	X	X	X	X	X	X	X	X	X	X	X	X	X ^j
Procedures and Nondrug Therapies ^j	X	X	X	X	X	X	X	X	X	X	X	X	X	X	X	X	X	X	X	X	X	X ^j

Study Week	Screening Period (Up to 6 Weeks) ^a	Dosing Period ^{a, b, c} (48 Weeks)																	Safety Follow-Up Period		
		Day 1 (First dose)	3	6	9	12	15	18	21	24	27	30	33	36	39	42	45	48/ Last dose/ET ^t	28 days after last dose ^f	60 days after last dose phone call ^r	
Assessment		Pre-dose	Post-dose																		
DLCO	X ^k																				
PFTs	X	X ^l		X ^l		X ^l		X ^l		X ^l				X ^l					X ^{l, t}		
HRCT of Chest	X ^m								X										X ^t		
SGRQ ⁿ		X				X			X					X					X ^t		
UCSD-SOBQ ⁿ		X				X			X					X					X ^t		
Leicester Cough Q ⁿ		X				X			X					X					X ^t		
Pregnancy Test (WOCBP) ^o	X	X		X	X	X	X	X	X	X	X	X	X	X	X	X	X	X	X ^p	X	X ^o
Assess vital status (in subject who terminate /withdraw from study early)										X ^q									X ^q		

Abbreviations: AE = adverse event; CBC = complete blood count; DLCO = diffusing capacity of the lungs for carbon monoxide; ECG = electrocardiogram; ET= Early Termination; hCG = human chorionic gonadotropin; HRCT = high resolution computed tomography; ICF = Informed Consent Form; PFTs = Pulmonary Function Test; SGRQ = Saint George’s Respiratory Questionnaire; UCSD-SOBQ = University of California San Diego – Shortness of Breath Questionnaire; WOCBP = Woman of child bearing potential; TB = Tuberculosis

- a.) Plans to re-screen a subject must be discussed with, and approved by, the Medical Monitor prior to re-screening.
- b.) Visit window of ±7 days, Week 3 through Week 48. The visit window of ±7 days also applies to assessments that cannot be performed on the same day; these assessments are considered part of that specific visit, and are to be labelled as such. Missed visits are not to be made up between scheduled visits, subject is to return for the next scheduled visit.
- c.) Unscheduled visit assessments (procedures) performed as necessary. During the COVID-19 pandemic, the visit modality (e.g.: in-person versus remotely) and scheduling maybe adjusted and conducted at the discretion of the Investigator, in accordance with the site’s rules and recommendations, and using all necessary precautions. If a visit has to be done remotely it can be conducted with any technology available to the site and study subjects.
- d.) Height is measured only at screening. Weight is measured at screening, Day 1(to calculate the starting dose), and every 12 weeks thereafter to determine the need for dose adjustment.
- e.) Additional PE’s may be performed as needed, if clinically indicated.

- f.) Additional ECGs may be performed as needed, if clinically indicated.
- g.) Study drug infusions are Q3W starting on Day 1. **NOTE:** infusions must be at least 10 days apart; missed doses are not to be made up between scheduled visits, subject is to return for the next scheduled visit/dose. Vital signs (blood pressure, pulse, and temperature) must be recorded prior to, and after each infusion, according to [Section 5.1.6](#).
- h.) If during a home infusion a new safety concern arises, the subject has to attend an on-site visit for an Investigator assessment as soon as feasible.
- i.) See Section 7 for details on safety assessments and AE/SAE reporting.
- j.) Concomitant medications and non-drug therapies must be reported starting with signing of informed consent and ending 28 days after the last dose. If the subject experiences an AE / SAE before the end of the final safety phone call (60 days after last dose), concomitant medications and non-drug therapies may also be collected, if part of the treatment of the AE/SAE.
- k.) If a DLCO is available within 3 months prior to screening, it can be utilized for screening purposes.
- l.) On-treatment PFTs, should be collected pre-dose.
- m.) If a recent HRCT scan (within 3 months prior to screening) is available, it can be utilized for screening purposes, provided it is submitted and evaluated by the Independent Radiology Imaging Review Group, is adhering to the same imaging acquisition parameters detailed in the Imaging Core Manual (ICM), and is either using the same accredited scanner, or is performed using the same modality, as the on-study HRCT scans.
- n.) Questionnaires are obtained pre-dose. On weeks where both questionnaires and PFTs are obtained, PFT should be completed first.
- o.) Pregnancy tests for woman of childbearing potential (WOCBP) only: serum pregnancy test at Screening; urine pregnancy tests (pre-dose) during study visits. A positive urine pregnancy test must be confirmed by serum hCG. At 60 days after last dose, a urine pregnancy test to be done at home by the subject (WOCBP) and report result to site. In each case of delayed menstrual period (over one month between menstruations) confirmation of absence of pregnancy is strongly recommended. This recommendation also applies to WOCBP with infrequent or irregular menstrual cycles.
- p.) Urine pregnancy test to be done at Week 48 visit for woman of child bearing potential only, who consent to OLE. A positive urine pregnancy test must be confirmed by serum hCG.
- q.) ET subjects will be contacted by phone at weeks 24 and 48 to check the subject's vital status.
- r.) All subjects will attend a visit 28 days after the last dose for all the marked assessments, and will be contacted by phone 60 days after the last dose, for a final safety assessment. Note: These two final safety assessments are to be scheduled after the last, final dose of study drug (e.g.: for subjects not progressing to the optional, OLE phase, the last dose is the one received during double blind phase; for subjects continuing in the OLE, it is the last pamrevlumab dose in the OLE phase). The visit window for safety follow up period are: 28 days + 7 days and 60 days + 7days (phone call) after the last dose. If the subject experiences an SAE during these 60 days, it must be reported within 24 hours of awareness (see Section 7.3 for details).
- s.) Subjects eligible for the OLE are to be consented for the OLE at or before the Week 48 visit
- t.) ET subjects: PFTs and Questionnaires do not have to be repeated if the last one was performed within 8 weeks (excluding the screening visit) of the ET visit. HRCT does not have to be repeated if the last one performed was within 4 months (excluding the screening visit) of the ET visit. Subjects who terminate / withdraw from the study early, for any reason, will have an Early Study Termination (ET) visit as soon as feasible. IP infusion will not be done at the ET visit.
- u.) **For Czech Republic only:** TB test done locally at screening only if none was performed within 6 months before screening for the study.
- v.) **For Czech Republic only:** For the first three infusions, the post-infusion observation period is 2 hours

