14. Daily use of PDE-5 inhibitor drugs (e.g. sildenafil, tadalafil) except for treatment of severe pulmonary artery hypertension.
15. Any current malignancy (this does not include localized cancer such as basal or squamous cell carcinoma of skin). Any history of malignancy likely to result in mortality, or requiring significant medical or surgical intervention within the next year.
16. History of allergic or anaphylactic reaction to human, humanized, chimeric or murine monoclonal antibodies, or to any component of the excipient.
17. Any condition (other than IPF) that is likely to result in the death of the patient within the next year.
18. Acute infection requiring any of the following:
 - a. Hospital admission for ≥ 24 hours within four weeks prior to screening, or during screening
 - b. Treatment with antibiotics (IV, IM, oral, or inhaled) within four weeks prior to screening, or during screening
 - c. Active or recent (≤ 4 weeks prior to randomization) upper or lower respiratory tract infection
 - d. Active tuberculosis requiring treatment within 12 months prior to screening

19. Known history of immunodeficiency, including but not limited to HIV infection.
20. Receipt of a live/attenuated vaccine within the four weeks prior to randomization.
21. Chronic treatment with any of the following within four weeks or five half-lives (whichever is longer) prior to randomization, if used to treat IPF:
 - a. Immunosuppressive or immunomodulatory therapies (e.g., azathioprine, cyclosporine A, cyclophosphamide, D-penicillamine, interferon-gamma, tumor necrosis factor- α antagonists)
 - b. Cytotoxic drugs (e.g., colchicine)
22. The Investigator judges that the subject will be unable to fully participate in the study and complete it for any reason, including inability to comply with study procedures and treatment, addiction, or any other relevant medical or psychiatric conditions.
23. Country Specific Criteria (Czech Republic Only): Positive result from a Tuberculosis (TB) screening test performed within 6 months prior to screening for the study. TB testing may be done locally.

STUDY TREATMENT

Dose and Mode of Administration:

Main Phase (Double-Blind, Placebo-Controlled):

Pamrevlumab or placebo, 30 mg/kg, IV, Day 1 and every 3 weeks thereafter, up to Week 48, for a total of up to 17 infusions.

Optional, Open Label Extension (OLE) Phase of Pamrevlumab:

Pamrevlumab (30 mg/kg) every 3 weeks

Other Important Information:

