3.3.1. Study Duration

Subjects are encouraged to receive all 17 study drug doses in the main study. Subjects who do not receive all doses are encouraged to continue with study visits and assessments.

Subjects who complete the Week 48 visit (regardless of the number of study drug doses received) will be eligible for an open-label, extension (OLE) phase, which will provide continuing access to pamrevlumab until the last subject completes 48 weeks of treatment in the OLE phase, or pamrevlumab is commercially available for the indication of IPF, or the Sponsor decides to end the OLE phase, whichever occurs first.

Subjects who withdraw from the main study early, for any reason, will have an Early Study Termination visit (ET) as soon as feasible. Study procedures to be performed during the ET visit can be found in the SOA (Appendix 1). These subjects will also have a safety follow up visit 28 days after the last dose, with a follow-up phone call 60 days after the last dose for a final safety assessment. Such subjects should also be contacted by phone at weeks 24 and 48 to check the subject's vital status. These subjects will not be eligible for the OLE phase

See also Section 4.3 for mandatory Study Withdrawal reasons, and Section 4.4 for procedures related to Early Study Withdrawal.

Figure 1: FGCL-3019-095 Study Schema

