- c.) Ensure subject has signed the informed consent at or before Week 48 visit of the main study and eligibility considerations have been assessed prior to EX Day 1 infusion.
- d.) Weight will be measured at EX Day 1 and every 24 weeks thereafter to determine dose for the subsequent 24-week interval.
- e.) Infusions must be at least 10 days apart. Vital signs (blood pressure, pulse, and temperature) must be recorded prior to, and after each infusion. The infusion durations and post-infusion observations periods have to be followed per Table 1 in Protocol Section 5.1.6, including the initial dosing and observations periods. Any home infusions via home health care are not permitted until at least three infusions in the OLE period have been administered without safety concerns. If a new safety concern arises during a home infusion, the subject has to attend an on-site visit for an Investigator assessment as soon as feasible.

- f.) See Section 7 of the main protocol for safety assessments.
- g.) Concomitant medications and nondrug therapies are recorded after signing of informed consent and ending 28 days after the last dose. If the subject experiences an AE or SAE before the end of the final safety phone call (60 days after last dose), concomitant medications and nondrug therapies may also be collected, if part of the treatment of the AE/SAE.
- h.) Local Labs and PFTs are performed pre-dose.
- i.) Collected according to local standard of care.
- j.) PFT will be done locally, and at a frequency per local SOC, and recorded on CRF whenever they are performed locally.
- k.) Labs will be done locally and at a frequency per local SOC. Lab data will NOT be recorded on CRF. Clinically significant laboratory abnormalities will be reported in the context of AE reporting; do not report non-clinically significant lab abnormalities as AE
- l.) HRCT scans will be performed at a frequency per local SOC. Any HRCT scan will be uploaded to central HRCT radiology vendor

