6.8.8. Pregnancy Test

Pregnancy tests for women of childbearing potential (WOCBP) only: serum pregnancy test at Screening; urine pregnancy tests (pre-dose) during study visits.

A listing of positive pregnancy test results during study visits will be provided.

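### Appendix 1 footnotes o and p are inconsistent on the Week 48 pregnancy test: p ties it to open-label extension consent, although Week 48 is a dosing visit whatever the extension decision

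*Protocol*

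**What the plan says.** **The testing rules.** The pregnancy-test row of Appendix 1 is marked at screening, at Day 1 before dosing, at each visit from Week 3 to Week 48, and at 28 and 60 days after the last dose. Footnote o is attached to the row label. For WOCBP it calls for "serum pregnancy test at Screening; urine pregnancy tests (pre-dose) during study visits", and it does not mention the OLE. Footnote p is attached to the Week 48 cell alone: "Urine pregnancy test to be done at Week 48 visit for woman of child bearing potential only, who consent to OLE". It then repeats a rule already in footnote o, that a positive urine result is confirmed by serum hCG.

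**The dosing rules.** The Synopsis gives dosing as "Day 1 and every 3 weeks thereafter, up to Week 48, for a total of up to 17 infusions", and section 3.3.1 says "Subjects are encouraged to receive all 17 study drug doses in the main study". The Week 48 column also serves early termination (ET). Footnote t takes the infusion away only there: "IP infusion will not be done at the ET visit".

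**OLE consent.** Appendix 1 footnote s says "Subjects eligible for the OLE are to be consented for the OLE at or before the Week 48 visit", and footnote c of the OLE schedule says "Ensure subject has signed the informed consent at or before Week 48 visit of the main study". The eligibility text of Appendix 6 is softer: consent must precede the first OLE dose, and having it by Week 48 is only a preference.

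**The SAP.** Section 6.8.8 of the double-blind SAP restates the general rule without an OLE condition: "Pregnancy tests for women of childbearing potential (WOCBP) only: serum pregnancy test at Screening; urine pregnancy tests (pre-dose) during study visits".

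**The concern.** Two instructions govern one cell of the schedule and do not agree. The pre-dose test is the scheduled check that a woman is not pregnant when study drug is infused. Pregnancy is an exclusion criterion (section 4.2) and a mandatory reason for withdrawal (section 4.3). Every other dosing visit has the test without conditions.

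The condition in footnote p also belongs to a different dose. OLE participation has no bearing on whether infusion 17 is given, and the OLE has its own pre-dose test at EX Day 1. If footnote p is applied as an override, women going on to the OLE are tested at Week 48 and again before their first OLE dose. A woman who declines the OLE, is judged unsuitable for it, or consents only after the Week 48 visit receives infusion 17 without a same-visit test. A pregnancy first detectable between Week 45 and Week 48 could then be followed by one avoidable dose.

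**Working it through.** **Inputs**
- Dosing on Day 1 and every 3 weeks up to Week 48, 17 infusions at most (Synopsis; section 3.3.1).
- Visit window ±7 days (Appendix 1, footnote b); infusions at least 10 days apart (footnote g).
- First safety follow-up: 28 days after the last dose, with a window of +7 days in footnote r and ±7 days in section 6.1.3.
- EX Day 1: 3 weeks ± 7 days after Week 48 (Appendix 6).

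**Step 1: is Week 48 a dosing visit?** Visits at weeks 0, 3, ..., 48 number 48/3 + 1 = 17, which reproduces the stated maximum. Without Week 48 there would be 16. Week 48 is therefore infusion 17, for every subject still on treatment who is not at an ET visit. Appendix 2 (PK samples before and after dosing at Week 48) and SAP Table 6 (Week 48 predose and postdose vital signs) agree.

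**Step 2: coverage under each reading**

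| Reading | Dosing visits with a scheduled pre-dose test, WOCBP without OLE consent |
|---|---|
| o and p applied together | 17 of 17 |
| p overrides o at Week 48 | 16 of 17 |

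**Step 3: time since the last scheduled test, if p overrides o.** Target days are 7 × 45 + 1 = 316 and 7 × 48 + 1 = 337, so the gap is 337 − 316 = 21 days. The longest gap within the windows is (337 + 7) − (316 − 7) = 344 − 309 = 35 days. The shortest is the 10-day minimum between infusions. This assumes that Week 45 was attended. The routine interval between tests is also 21 days (10 to 35), so what is lost is the check before the dose.

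**Step 4: time to the next scheduled test**
- Not entering the OLE: 28 days after the dose by target. Footnote r gives 28 to 28 + 7 = 35 days; section 6.1.3 gives 28 − 7 = 21 to 35 days.
- Consenting after Week 48 and entering the OLE: EX Day 1, at 21 ± 7 = 14 to 28 days.

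**Step 5: does the OLE condition serve the OLE dose?** The OLE schedule already requires a pre-dose test at EX Day 1, so entry to the OLE does not depend on the Week 48 test.

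**The case against.** The strongest reply is that nothing is waived. Footnote o governs the whole row, the Week 48 cell is marked, and footnote p never says that women outside the OLE go untested. Where Appendix 1 does lift a requirement, it says so openly, as footnote t does for repeat assessments and for the ET infusion. On that reading o still requires the test. This stands, and it means that the omission is possible, not certain. It does not remove the inconsistency: if o already covers everyone, the OLE condition in p has no function, and a site could reasonably take the note attached to the specific cell as controlling.

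Three narrower points also stand.
- SAP 6.8.8 introduces a listing of positive results and does not direct sites. It supports the general rule but adds no second requirement.
- Footnote b lets an assessment that cannot be done on the same day fall within the visit window. The loss is therefore of a same-visit test, not strictly a same-day one.
- Because Appendix 6 allows OLE consent after Week 48, the affected group cannot be limited to women who decline the OLE or are ineligible for it.

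A reader might infer that the protocol exempts women outside the OLE from testing, or exposes them to a material fetal risk. The documents support neither. Their tests at 28 and 60 days after the last dose remain. Section 5.2.3 requires highly effective contraception, strongly recommends a check when menses are more than a month late, and reports the rabbit abnormalities at about 20 times human exposure. Half of subjects receive placebo.

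**Conclusion.** The inconsistency is real and minor. Footnote p sets a condition that conflicts with footnote o and is unrelated to the dose given at that visit, and no reason is stated for it. The consequence depends on a site letting p override o. In that case one of 17 infusions could be given without a same-visit test to a WOCBP who has not consented to the OLE, with the last scheduled test 21 days before the dose by target.

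The documents give no count of WOCBP. With an entry age of 40 to 85, and most IPF patients 60 or older at diagnosis (section 2.2), few women are likely to be affected. Confidence is high that the two footnotes disagree; it does not extend to any likelihood of harm. No efficacy result, sample size or error rate is touched.

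**What to change.** In Appendix 1 footnote p, delete the closing clause that makes the Week 48 test conditional on OLE consent, so that every WOCBP attending Week 48 is tested. Add that the test is done before dosing when an infusion is given at that visit.

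Do not limit the test to women being dosed. OLE eligibility depends on completing the Week 48 visit, whatever the number of infusions received. A WOCBP who has stopped study drug, attends Week 48 and consents to the OLE is tested under the present footnote, and would lose that test under such a limit (EX Day 1 would still cover her).

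The cost is one footnote edit and one urine test in very few women. The SAP, the endpoints and the visit schedule do not change.
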